#### 9.4.3.2. Pharmacokinetic Analysis on Urine Samples

For urine samples, the following pharmacokinetic parameters will be derived for JNJ-56136379 and/or NA (ETV or TDF), as applicable:

- On Day 1 (**for NA in Treatment Arms 4-5 and 9-10 only**):  $CL_R$
- On Day 84 (Week 12):  $CL_R$

For urine-derived parameters, definitions and methods of calculation are:

- $Ae_{x-y}$  amount of unchanged drug excreted into urine over a given time interval, calculated from the urinary drug concentration of the collection interval x to y hours postdose multiplied with the associated

---

	urine volume of the interval
• Ae total	total amount of unchanged drug excreted into urine, calculated by adding the amounts of the individual intervals together
• Ae,%Dose	total percentage of the dose excreted into urine as unchanged drug, calculated as 100*(Ae total /Dose)
• CL R	renal clearance, calculated as Ae total /AUC ∞ or Ae τ /AUC τ at steady-state

## 9.5. Pharmacokinetic/Pharmacodynamic Evaluations

Relationships of pharmacokinetic parameters for JNJ-56136379 and NA (ETV or TDF), as applicable, with selected efficacy and with selected safety endpoints will be evaluated.

## 9.6. Biomarkers

The study includes collection of blood samples for exploratory analysis of host blood biomarkers at the host mRNA, protein, and cell level. Sampling will be performed in all subjects at the time points indicated in the [TIME AND EVENTS SCHEDULE](#).

Phenotypic and functional characterization of the immune response may be performed using immune cell-based assays. Samples for these analyses will be obtained at selected sites only.

Samples can only be used for research related to JNJ-56136379, NA (ETV or TDF), CHB infection, or HBV-related disease or may be used to develop tests/assays related to JNJ-56136379, NA (ETV or TDF), or HBV.

These analyses will be performed at the sponsor's discretion, will always be under the sponsor's supervision, and may be reported separately from the main study report.

## 9.7. Pharmacogenomic (DNA) Evaluations

A blood sample for pharmacogenomics (DNA) research will be taken, preferentially at baseline. This sample is optional and will only be collected from subjects who consent separately to this component of the study. This sample can be used to investigate the potential association of genetic factors with efficacy, safety, or pharmacokinetics of JNJ-56136379, NA (ETV or TDF), CHB infection, or HBV-related disease or may be used to develop tests/assays related to JNJ-56136379, NA (ETV or TDF), or HBV.

These analyses will be performed at the sponsor's discretion, will always be under the sponsor's supervision, and may be reported separately.

## 9.8. Patient-Reported Outcomes

The impact of HBV treatment on subjects, including symptoms, functioning and HRQoL will be assessed using PROs at predefined time points. The following PRO instruments will be used: EQ-5D-5L, HBQOL, MOS-CFS Cog-R, and SF-36v2 (see [Attachment 4](#), [Attachment 5](#), [Attachment 6](#), and [Attachment 7](#), respectively).

PRO assessments will be performed by all subjects at sites where appropriate translations are available. Subjects should complete these assessments in their native language or if there is no version available in their native language, a version in a language in which the subject is fluent and literate. It is preferable that subjects are able to read and write to complete the assessments by themselves. If a subject is unable to read or has visual or other physical limitations that make it difficult to read or complete the assessments, trained study-site personnel may read the questions and responses aloud exactly as they appear on the assessment and record the subject's responses.

Study-site personnel will record in the eCRF whether the PRO assessments were performed during the study visit.

Subjects will complete the PRO assessments electronically during study site visits on a touch-screen tablet provided for this study. The subject should be provided a quiet place to complete the PRO assessments, and instructed how to complete the PRO assessment on the tablet. When deciding which answer to report, subjects should not receive any help from anyone accompanying them (such as family members and friends) or study-site personnel; the responses should reflect the subject's interpretation and response.

Subjects' responses to the PRO questionnaires will not be reported as AEs or SAEs.

### **5-level EuroQol 5-Dimension**

The EQ-5D-5L questionnaire is a brief, 2-page, generic HRQoL assessment that evaluates a subject's self-rated health state on 5 dimensions (mobility, self-care, usual activities, pain/discomfort, anxiety/depression). Additionally, a Visual Analog Scale (VAS) records the subject's self-rated health on a vertical VAS where the endpoints are labelled 'best imaginable health state' (100) and 'worst imaginable health state' (0). This information can be used as a quantitative measure of health outcome as judged by the subject. EQ-5D scores include the following:

- EQ-5D Valuation Index score (a weighted scoring of the 5 dimension scores with a possible range from 0 to 1);
- EQ-5D VAS score (with a possible range from 0 [worst imaginable health] to 100 [best imaginable health]);
- EQ-5D descriptive system scores (5 scores reflecting each of the 5 dimensions ranging from 0 [no limitation] to 4 [incapacity]).

It takes about 2 minutes to complete the EQ-5D-5L questionnaire. See [Attachment 4](#) for a representative example of the EQ-5D-5L.

## **Hepatitis B Quality of Life**

The HBQOL version 1 is a 31-item disease-specific instrument designed to measure HRQoL for subjects with CHB. The instrument includes 7 subscales/domains, including psychological well-being, anticipation anxiety, vitality, stigma, vulnerability, transmission, and viral response. Each of the 31 items is scored on a 5-level response scale. Each subscale score is simply calculated as the average score among the items included in that subscale. In addition to the 7 subscales, there is a single global score that reflects the results on all 31 items. The global score is simply the average score among all the items in the HBQOL. Responses are transformed along a 0 to 100-point scale, where lower scores denote less HRQoL impact, and higher scores denote more HRQoL impact (ie, 0=best score; 100=worst score).

It takes about 10 minutes to complete the HBQOL version 1. See [Attachment 5](#) for a representative example of the HBQOL version 1.

## **Medical Outcomes Study Cognitive Functioning Scale-Revised**

The MOS-CFS Cog-R is a patient-reported instrument that measures a range of cognitive functions using the following 6 items: having difficulty in reasoning and solving problems (eg, making decisions), having difficulty doing activities involving concentration and thinking, becoming confused and starting several actions at a time, forgetting things that happened recently, having trouble keeping attention on any activity for a longer time, and reacting slowly to things that are said or done. The response options for each of the items are on a 5-point scale (all, most, some, a little, or none of the time). Responses for all items yield a single overall score.

It takes about 2 minutes to complete the MOS-CFS Cog-R questionnaire. See [Attachment 6](#) for a representative example of the MOS-CFS Cog-R.

## **Short Form 36 version 2**

SF-36v2 is a generic 36-item instrument designed to measure health status that can be interpreted using 2 summary scores – Physical Component Summary (PCS) and Mental Component Summary (MCS) – as well as domain subscales. The SF-36v2 consists of 8 subscales. Although SF-36v2 PCS and MCS scores include information from all 8 SF-36 domain subscales, the PCS score gives more weight to physical aspects of HRQoL as represented in the Physical functioning, Physical role limitations, Pain, and General health perception domain scores. The MCS score gives more weight to the emotional and social aspects of HRQoL as assessed by the Vitality, Social function, Social role limitations, and Mental health domain scores. Participants self-report on items that have between 2-6 response options per item using Likert-type responses (eg, none of the time, some of the time, etc.). Summations of item scores of the same subscale give the subscale scores, which are transformed into a range from 0 to 100; 0=worst HRQoL, 100=best HRQoL. PCS and MCS scores are constructed as a T-score with a mean of 50 and SD of 10; higher scores indicate better health status. The 4-week recall version will be used.

It takes about 10 minutes to complete the SF-36v2 questionnaire. See [Attachment 7](#) for a representative example of the SF-36v2.

## **9.9. Safety Evaluations**

Safety and tolerability will be assessed throughout the study from the time that the ICF is signed until the completion of the last study-related activity. The evaluations of safety and tolerability will include monitoring of (S)AEs, physical examinations, vital signs measurements, 12-lead ECGs, and clinical laboratory tests (including hematology, blood biochemistry, blood coagulation, and urinalysis) at predefined time points as specified in the [TIME AND EVENTS SCHEDULE](#).

Specific toxicity management plans in line with the known pharmacological profile of the study drugs (and the drug classes) evaluated in this study will be implemented.

Any clinically significant abnormalities persisting at the end of the study/early withdrawal will be followed by the investigator until resolution or until a clinically stable endpoint is reached.

Details regarding the DRC are provided in Section [11.12](#).

Any clinically relevant changes occurring during the study must be recorded in the AE section of the eCRF.

The study will include the following evaluations of safety and tolerability according to the time points provided in the [TIME AND EVENTS SCHEDULE](#):

### **Adverse Events**

Adverse events will be reported by the subject for the duration of the study. Adverse events will be followed by the investigator as specified in Section [12](#).

Special attention will be paid to those subjects who discontinue the study for an AE, or who experience an AE of at least grade 3, or an SAE.

### **Clinical Laboratory Tests**

Blood samples for serum chemistry and hematology and a urine sample for urinalysis will be collected. The investigator must review the laboratory results, document this review, and record any clinically relevant changes occurring during the study in the AE section of the eCRF. The laboratory reports must be filed with the source documents.

Subjects need to have fasted for at least 10 hours before biochemistry samples are taken for measurement of phosphorus, calcium, creatinine clearance, and lipids. Subjects should bring their study drug with them to each visit and have that day's intake at the site.

In case a grade 3 or grade 4 laboratory abnormality occurs, a confirmatory test must be performed preferably within 48 hours but no later than 72 hours after the results have become available.

The following tests will be performed by the selected laboratory:

- Hematology Panel
 

-hemoglobin	-WBC differential (including %)
-hematocrit	*neutrophils
-red blood cell (RBC) count	*lymphocytes
-RBC parameters	*monocytes
*mean corpuscular hemoglobin (MCH)	*eosinophils
*MCH concentration	*basophils
*mean corpuscular volume	-platelet count
-white blood cell (WBC) count with differential	

A WBC evaluation may include any abnormal cells, which will then be reported by the laboratory. A RBC evaluation may include abnormalities in the RBC count, RBC parameters, or RBC morphology, which will then be reported by the laboratory. In addition, any other abnormal cells in a blood smear will also be reported.

- Serum Chemistry Panel
 

-sodium	-calcium
-potassium	-phosphate
-chloride	-albumin
-bicarbonate	-total protein
-blood urea nitrogen	-total cholesterol
-creatinine	-high-density lipoprotein cholesterol
-glucose	-low-density lipoprotein cholesterol
-AST	-triglycerides
-ALT	-magnesium
-gamma-glutamyltransferase	- $\alpha_1$ -acid glycoprotein
-total, conjugated and unconjugated bilirubin	-calculated creatinine clearance (by MDRD formula)
-alkaline phosphatase	-lipase
-creatine phosphokinase	-amylase (reflex testing of pancreatic amylase should be done in case of post-screening amylase or lipase increase)
-lactic acid dehydrogenase	-fibrinogen (on blood)
-uric acid	-C-reactive protein

- Urinalysis

A urine sample must be provided for urinalysis. Specific gravity, pH, glucose, protein, blood, ketones, bilirubin, urobilinogen, nitrite, and leukocyte esterase will be determined using dipstick. In case of positive dipstick results, the sediment will be examined microscopically for RBCs, WBCs, and epithelial cells and an additional examination will be performed on the positive urinary parameter (eg, quantification as applicable). Crystals, casts and bacteria will only be reported if they are present.

- At screening, a serum pregnancy test will be performed for women of childbearing potential.
- At screening, an FSH test will be performed for postmenopausal women.

- At time points as indicated in the **TIME AND EVENTS SCHEDULE**, a urine pregnancy test will be performed (women of childbearing potential only).
- At screening, a HIV-1 and -2 test, and hepatitis A, B, C, D, and E tests will be performed.
- At screening and time points as indicated in the **TIME AND EVENTS SCHEDULE**, tests will be performed for HBsAg, HBeAg, HBcAg, and anti-HBs and anti-HBe antibodies.
- At screening and time points as indicated in the **TIME AND EVENTS SCHEDULE**, determination of coagulation parameters will be performed. INR will be calculated by the central laboratory.
- At screening, alpha-fetoprotein will be measured.

In case of **rash**, blood samples (mandatory blood sample for safety in case of Grade 3 or Grade 4 rash and at the discretion of the investigator in case of Grade 1 or Grade 2 rash) need to be taken for safety laboratory testing, and are to be processed by the local laboratory. These samples need to be taken at unscheduled visits as described in [Attachment 3](#). The following parameters need to be tested: AST, ALT, erythrocyte sedimentation rate, creatinine, and a complete blood cell count (including hemoglobin, hematocrit, RBC count, WBC count, neutrophils, lymphocytes, monocytes, eosinophils, basophils, and platelet count).

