***Rash***

For subjects reporting rash, please see [Attachment 3](#).

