***Acute Systemic Allergic Reactions*****Grade 1 (Localized Urticaria [Wheals] With no Medical Intervention Indicated)**

Subjects may continue the intake of study drugs.

Cetirizine, levocetirizine, topical corticosteroids or antipruritic agents may be prescribed.

Subjects should be advised to contact the investigator immediately if there is any worsening of the acute systemic allergic reaction.

**Grade 2 (Localized Urticaria With Medical Intervention Indicated, or Mild Angioedema With no Medical Intervention Indicated)**

Subjects may continue the intake of study drugs.

Cetirizine, levocetirizine, topical corticosteroids or antipruritic agents may be prescribed.

Subjects should be advised to contact the investigator immediately if there is any worsening of the acute systemic allergic reaction, in which case the subject will permanently discontinue the intake of JNJ-56136379. Rechallenge is not allowed. The subject's NA treatment may be discontinued based on investigator judgement in consultation with the sponsor.

**Grade 3 (Generalized Urticaria, Angioedema With Medical Intervention Indicated, or Symptomatic Mild Bronchospasm) and Grade 4 (Acute Anaphylaxis, Life-Threatening Bronchospasm, or Laryngeal Edema)**

Subjects will permanently discontinue the intake of JNJ-56136379. Rechallenge is not allowed. The subject's NA treatment may be discontinued based on investigator judgement in consultation with the sponsor.

Subjects will be treated as clinically appropriate. Subjects should be followed until resolution of the AE and standard management should be undertaken.

***AST and ALT Elevation*****Grade 1 ( $\geq 1.25$  to  $<2.50 \times$  ULN), or Grade 2 ( $\geq 2.50$  to  $<5.00 \times$  ULN)**

Subjects may continue the intake of study drugs.

Subjects should be followed until resolution (return to baseline) or stabilization of AST/ALT elevation (to be agreed upon with the sponsor).

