**Attachment 3: Rash Management**

For subjects reporting rash, the following should be done.

**Subjects should be informed that they should contact their doctor immediately when they notice any skin reaction. The skin reaction should be evaluated in the clinic the same day (if possible) or the next day.**

All rash events should be captured in the AE section of the eCRF. A separate Rash page will be completed in case of a rash event.

Grading of rash events will be based on the DAIDS Toxicity Grading Scale.

Monitoring of the evolution of rash events will be performed as described in [Table 8](#).

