**Table 8: Management of Rash Events by Severity Grade**

	Definition	Study Drug Action	Activities by Daya	Referral to Dermatologist and Dermatology Activities
Grade 1 rash (with or without pruritus)b	Erythema	Study drug intake may be continued at the investigator's discretion	
Day 0: optional on site visit for initial rash evaluation may be performed at the investigator's discretion.
 
Safety laboratory assessments may be performed at the investigator's discretion (recommended if visit occurs).
 
Digital pictures* of skin lesions may be taken at the investigator's discretion.
 
Determine if subject was adhering to the recommended sun-protective measures. If appropriate, provide sun protection counseling.
 
Day 1 and thereafter: appropriate follow-up visits at the investigator's discretion until resolution of rash.
 
Safety laboratory assessments and photography (digital pictures* of skin lesions) may be performed at the investigator's discretion.
	Not required
Grade 2 rash (with or without pruritus)b	Diffuse, maculopapular rash, or dry desquamation	Study drug intake may be continued at the investigator's discretion	
Day 0: required on-site visit (if a visit is not possible, telephone contact with the subject should take place to collect information and give advice on the necessary measures to be taken).
 
Safety laboratory assessments may be performed at the investigator's
	
Referral to dermatologist at the discretion of the investigatorc
 
Biopsy not required, but may be performed at the dermatologist's

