**Table 8: Management of Rash Events by Severity Grade**

Definition	Study Drug Action	Activities by Day a	Referral to Dermatologist and Dermatology Activities
		
discretion (recommended).
 
Digital pictures* of skin lesions may be taken at the investigator's discretion.
 
Digital pictures* of skin lesions are recommended in case consultation of a dermatologist is required. Determine if subject was adhering to the recommended sun-protective measures.
 
If appropriate, provide sun protection counseling.
 
Day 1 and thereafter: appropriate follow-up visits at the investigator's discretion until resolution of rash or until clinical stability is reached.
 
Safety laboratory assessments are required on Day 1 and are required thereafter only if the previous values were abnormal (but may be performed at the investigator's discretion). If the rash progresses to a higher grade, safety laboratory assessments of the higher grade should be followed.
 
Digital pictures* of skin lesions may be taken at the investigator's discretion.
	discretion

\* Digital pictures to be taken at the clinical site.

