**Table 8: Management of Rash Events by Severity Grade**

	Definition	Study Drug Action	Activities by Daya	Referral to Dermatologist and Dermatology Activities
Grade 3 rashb	
Vesiculation, moist desquamation, or ulceration OR
 
Any cutaneous event with 1 of the following:
 
 
- Elevations in AST/ALT <math>>2\times</math>baseline value
 
- Fever <math>>38^{\circ}\text{C}</math> or <math>100^{\circ}\text{F}</math>
 
- Eosinophils <math>>1.00\times 10^3/\mu\text{L}</math>
 
- Serum sickness-like reaction
 
	
Must permanently discontinue JNJ-56136379; no rechallenge allowed
 
NA treatment may be discontinued based on investigator judgement in consultation with the sponsor
	
Day 0: required on-site visit. Safety laboratory assessments required to be performed. Digital pictures* of skin lesions may be taken at the investigator's discretion (recommended). Determine if subject was adhering to the recommended sun-protective measures. If appropriate, provide sun protection counseling.
 
Day 1: required on-site visit. Safety laboratory assessments required to be performed. Digital pictures* of skin lesions may be taken at the investigator's discretion (recommended).
 
Further visit(s): appropriate follow-up required until resolution of rash or until clinical stability is reached.
 
Safety laboratory assessments and photography (digital pictures* of skin lesions) are recommended to be performed until the rash severity resolves to Grade 2 or Grade 1.
	
Requiredc
 
Biopsy not required, but may be performed at the dermatologist's discretion.

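### Protocol 9.9 makes Grade 2 rash blood samples optional, while Attachment 3 Table 8 requires them on Day 1 and again after abnormal values

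*Protocol*

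**What the plan says.** Protocol 9.9, Clinical Laboratory Tests, makes safety blood samples mandatory for Grade 3 and Grade 4 rash and leaves them "at the discretion of the investigator in case of Grade 1 or Grade 2 rash". The next sentence of that paragraph refers to Attachment 3 for the unscheduled visits at which samples are drawn. Under Specific Toxicities, 9.9 again says "For subjects reporting rash, please see" Attachment 3. Attachment 3 in turn states "Monitoring of the evolution of rash events will be performed as described in" Table 8.

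The Grade 2 row of Table 8 sets this schedule:

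- Day 0 visit: "required on-site visit (if a visit is not possible, telephone contact with the subject should take place to collect information" and give advice. The Day 0 blood sample is discretionary but recommended.
- From Day 1, visits: "appropriate follow-up visits at the investigator's discretion until resolution of rash or until clinical stability is reached".
- From Day 1, blood: "Safety laboratory assessments are required on Day 1 and are required thereafter only if the previous values were abnormal". A closing parenthesis allows further samples at the investigator's discretion.

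The Grade 3 row includes two criteria that only a blood test can show: AST/ALT above twice baseline, and eosinophils above 1.00×10^3/µL. The drug action for that grade is "Must permanently discontinue JNJ-56136379; no rechallenge allowed". Protocol 10.2, item 4, repeats the mandatory stop for rash of Grade 3 or higher.

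**The concern.** The two texts give different rules for the same sample. Under 9.9 an investigator may take no blood at any point of a Grade 2 rash. Under Table 8 that is a deviation on Day 1.

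The sample decides the grade. A rash that looks Grade 2 on the skin is Grade 3 if the enzymes or eosinophils have crossed the limits, and the drug must then stop for good. A site working from the 9.9 parenthesis would not have that result and could keep the subject on JNJ-56136379. The stake is the safety of individual subjects and consistent conduct across sites; the primary endpoint and its analysis are not affected.

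**Working it through.** **Side by side**

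| Situation | Protocol 9.9 | Table 8 | Agree? |
|---|---|---|---|
| Grade 1, any day | discretionary | discretionary | yes |
| Grade 2, Day 0 | discretionary | discretionary, recommended | nearly |
| Grade 2, Day 1 | discretionary | required | **no** |
| Grade 2, later, previous values abnormal | discretionary | required | **no** |
| Grade 3–4, Days 0 and 1 | mandatory | required | yes |

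The conflict is confined to Grade 2 rash from Day 1 onward.

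**Would another rule catch the laboratory-only trigger?** Assume, for illustration, an untreated subject with baseline ALT 1.5 × ULN and a Grade 2 rash.

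- Table 8 trigger: 2 × 1.5 = 3.0 × ULN. ALT of 3.5 × ULN is 3.5 / 1.5 = 2.33 × baseline, so the rash is Grade 3 and the drug must stop.
- The AST/ALT rules in 9.9: 3.5 × ULN is a Grade 2 elevation (2.50 to below 5.00 × ULN), with which study drugs may continue.
- Protocol 10.2, item 7: needs ALT above twice baseline together with a direct bilirubin, INR or albumin abnormality.
- Even at Grade 3–4 ALT, 9.9 asks only for contact with the sponsor in defined cases, and 10.2, item 6, exempts ALT/AST.
- Protocol 10.2, item 2, stops treatment if the investigator judges this best for safety, but a laboratory reason requires a result to act on.

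**How long could it go unseen?** Chemistry and haematology are drawn at every scheduled treatment visit. From Week 4 these are 28 days apart. Day 0 is the first day of investigator assessment. Let the last scheduled visit be day v and Day 0 be day v + k. The Table 8 sample is then due on day v + k + 1, and the delay to the next scheduled sample is 28 − (k + 1) = 27 − k days.

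- k = 0 (Day 0 on a scheduled visit): 27 days. The scheduled sample is drawn that day, so this case needs the values to cross the limit between that draw and Day 1.
- k = 1: 26 days.
- k = 27: 0 days. If k is taken as uniform on 0 to 27, the mean is 27 / 2 = 13.5 days.
- Visit windows (±2 days through Week 4, ±5 days after) can stretch the gap. Weeks 4 to 8: 28 + 2 + 5 = 35 days, delay 35 − 1 = 34. From Week 8: 28 + 5 + 5 = 38 days, delay 38 − 1 = 37.
- Before Week 4: a 7-day gap gives at most 6 days, a 14-day gap at most 13.

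**SAP rash appendices**

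| Item | SAP Appendix 9 | Other texts |
|---|---|---|
| Grade 2 drug action | permanent stop | may continue at the investigator's discretion (SAP Appendix 10, Protocol Table 8) |
| Study withdrawal | Grades 2, 3 and 4 withdrawn | only loss to follow-up, consent withdrawal or death (Protocol 10.2) |
| Laboratory Grade 3 (AST/ALT) | above 2 × baseline and at least 5 × ULN | above 2 × baseline alone (SAP Appendix 10, Protocol Table 8) |

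The example above, ALT 3.5 × ULN, is Grade 3 under SAP Appendix 10 but not under SAP Appendix 9. SAP 6.1 plans a rash listing by specific grade and points to an appendix without a number, so it does not say which definition applies.

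**The case against.** The best defence is the pointer. The sentence immediately after the disputed parenthesis sends the reader to Attachment 3, and two further references lead to Table 8. A site would have to stop reading early to miss the Day 1 rule. This stands as a reason to expect few misses. It does not reconcile the rules, because 9.9 itself says that Grade 2 samples are discretionary.

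The delay is also conditional. It needs a trigger visible only in blood, no clinical Grade 3 sign, a recommended Day 0 sample not taken or still below the limits, no discretionary sample afterwards, and no early return. Table 8 tells subjects to report worsening, systemic signs or mucosal involvement at once, and Attachment 3 asks for clinic evaluation the same or next day. All of this is fair, and the delay should not be read as typical.

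A reader might infer that Table 8 defeats its own requirement because visits from Day 1 are discretionary. The documents do not support that: a required sample implies that the subject is seen, and the discretion can be read as covering the number and timing of follow-up visits. The wording could be clearer, as in the Grade 3 row, which states the Day 1 visit outright. Nor does the closing parenthesis on discretion cancel Day 1. It most naturally permits extra samples after normal values.

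Finally, no document says which rule is intended. Making the Day 1 sample discretionary in Table 8 would also remove the conflict. Table 8 is the more specific text, however, both pointers lead to it, and SAP Appendix 10 repeats its requirement.

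**Conclusion.** The inconsistency is in the current protocol text and should be corrected. For Grade 2 rash from Day 1, 9.9 permits what Table 8 forbids, and the sample concerned is the only means of detecting the two laboratory triggers for a permanent stop. If no discretionary sample is taken, detection could be delayed by up to about 4 weeks from Week 4 on (27 days at nominal spacing), and by less before Week 4.

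That figure is a worst case under the conditions stated. The documents give no Grade 2 rash rate and no rate of laboratory-only triggers, so neither an expected number of subjects nor an expected excess exposure can be derived. A reader might also infer that Grade 2 rash is unmonitored, or that Grade 3–4 rash is affected. Neither follows: the texts agree on Grades 3–4, and clinical Grade 3 signs need no blood sample.

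The SAP conflict is secondary. It could change which events the rash listing shows as Grade 3, but it does not bear on efficacy results.

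**What to change.** 1. **Protocol 9.9.** Replace the rash parenthesis with a sentence to this effect: *Safety blood samples are mandatory for Grade 3 or 4 rash and, for Grade 2 rash, on Day 1 and thereafter while the previous values are abnormal; otherwise they are discretionary, as set out in Attachment 3, Table 8.*
2. **Table 8, Grade 2 row (minor clarification).** State that a Day 1 on-site or local-laboratory contact is needed for the required sample. Leave later visits to the investigator except where a repeat sample is required.
3. **SAP.** Delete Appendix 9 and point the rash listing in SAP 6.1 to Appendix 10 by number. The opening line of Appendix 10 refers back to the text above it and needs a small edit.

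The cost is one sentence and one phrase in the protocol, plus the removal of one SAP appendix with its references tidied. Table 8 already requires the Day 1 sample, so no new procedure is added; the contact to obtain it simply becomes explicit.
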